ACCORDS

ADULT AND CHILD CENTER FOR OUTCOMES
RESEARCH AND DELIVERY SCIENCE

UNIVERSITY OF COLORADO
CHILDREN'S HOSPITAL COLORADO

Supporting the implementation of a state policy on screening for Adverse Childhood Experiences (ACEs) in Federally Qualified Health Centers.

Study Protocol Document

NCT: 04916587

Date: 07.20.2024

COMIRB Protocol

COLORADO MULTIPLE INSTITUTIONAL REVIEW BOARD
[name] [contact] [contact]

Protocol #: 22-0547

Project Title: Supporting the implementation of a state policy on screening for Adverse Childhood Experiences (ACEs) in Federally Qualified Health Centers.

Principal Investigator: [name] [name].

Version Date: 05/10/2024

I. Background/Rationale [previously iStar section 11 (exempt) or 12 (expedited/full board)]

Background

- Adverse Childhood Experiences (ACEs) refer to traumatic events occurring before age 18, such as maltreatment, family separation and exposure to violence.
- ACEs are pervasive among children ages 0 – 17 years old in the United States with 45% experiencing at least one ACE and 10% experiencing three or more ACEs. These events place children at high risk for negative life outcomes if left undetected and untreated.
- Early screening for ACEs is a national public health priority but health care providers seldom use these screenings during routine wellness checks.
- This study leverages the Surgeon General of the state of California's 2020 ACEs screening policy (ACEs Aware), which is supported by an annual \$40.8 million budget. Starting January 2020, the state's Medicaid health care program will reimburse primary care settings for implementing ACEs screenings annually during well-child visits.

Justification

- There is evidence that increased mental health screening campaigns alone often do not translate into higher access to services for children and they may in fact exacerbate disparities by increasing stigma and reinforcing a deficit view of marginalized groups.
- One reason why these efforts do not meet expected outcomes is the fact that they lack an evidence-based implementation plan to successfully deliver the screening programs/policies in local contexts.
- This study is needed to fill that gap as, in partnership with a trauma-informed workgroup, we will develop and test implementation strategies suited for pediatric screening in community-based health centers in California.
- Results of our study will inform our clinical partners and state policy leaders on their efforts to promote the successful adoption and implementation of the ACEs Aware state policy.

II. Purpose/Objectives/Aims/Research Questions

- This study will test the implementation strategy and examine its impact on the fidelity and reach of ACEs screenings (implementation outcomes), the resulting linkage to support services, and any changes in children's clinical screening scores (i.e., Pediatric Symptoms Checklist) as a result of families being linked to support services.
- The implementation strategy is comprised of the following activities:
 - **Activity 1: Short video-trainings** for clinic personnel (care team staff and providers) on the administration of caregiver-reported screening tools through a trauma-informed care lens and implementation protocols. The trainings will complement the current state-sponsored 2-hour on-line provider training and related trainings currently implemented at the FQHC.
 - **Activity 2: Technical implementation support** using a combined approach comprised of external academic consultants and internal FQHC personnel to increase its internal capacity. Each clinic will receive intense implementation support from the FQHC implementation coach (about 1 hour

per week virtual or in person in the first 10-week trial crossover period), and less intense support in the succeeding 10-week periods (45-60 minutes every other week visit and phone consult). In addition, the Trauma Informed Care (TIC) workgroup, comprised of FQHC leadership (i.e., clinical and quality departments), service providers, communications director, information technology (IT) coordinator, and academic collaborators will support clinics.

- **Activity 3: Use of a validated clinical screening tool** — The Pediatric Symptoms Checklist (PSC) is used in pediatric primary care settings to assess behavioral and social/emotional development. For this study, we will use the PSC tool tailored to children ages 0 to 5 years old. The PSC screening tool is needed, as the ACEs screening called PEARLS only assesses ACEs exposure and not mental health needs, which is a common ACEs sequela.
- **Activity 4: Use of a technology-based tailored screening algorithm** that will be made available to ACEs screeners using computer tablets. The algorithm will be hosted in a HIPAA compliant REDCap (Research Electronic Data Capture) secure web application, hosted at the PI's institution, to facilitate the screening process.
- Examine the value of pairing the delivery of a state policy with an implementation plan tailored to community-based clinics.
- Convene a diverse workgroup comprised of researchers, health care personnel and patients to refine an implementation strategy designed to support the ACEs state screening policy in community-based clinics.
- Pilot test the feasibility, acceptability, fidelity, and reach (i.e., number of ACEs screenings delivered divided by the total number of eligible child visits to their clinic in a 10-week period) of the developed implementation plan.
- Compare changes in child referrals to mental health services, after caregivers' participation in the screenings, between intervention and comparison clinics.
- Compare changes in PSC scores before and after caregivers' participation in the screenings:
Ten weeks after child's initial screening, a member of the study research team will contact a group of caregivers (n=100) on the phone to implement the Pediatric Symptoms checklist (post) and assess any changes from scores obtained during the initial screening at the clinic (pre). The study statistician will randomly select 35 caregivers from each study clinic who participated in the study (the goal is to interview 20 caregivers x 5 clinical sites), and create a separate database in REDCap with the list of selected caregivers and the phone number provided in the consent form. Research study team members will use the list to contact caregivers to schedule phone interviews. We will use this database to track completed interviews, declines, and not being able to contact. The statistician will replenish the list as needed.

III. Participants (sample) (Consistent with iStar sections 10 (expedited and full board) and 22 (for all submission types))

a. Inclusion and exclusion criteria for enrollment:

Inclusion criteria. Clinic eligibility is defined by: provision of pediatric care (i.e., family medicine, pediatric, primary care) for child patients ages 0-5 years old. Caregiver eligibility for reporting of the PEARLS and Pediatric Symptoms Checklist (PSC) on their child's behalf and interviews: Adults ages 18 years and older with legal custody or with the authority to arrange care for the child. Clinic staff eligibility for interviews: Clinic personnel involved directly or indirectly in the planning and/or implementation of the ACEs Aware policy.

Exclusion criteria. Clinics not providing pediatric care (i.e., family medicine, pediatric, primary care) for child patients ages 0-5 years old. Caregivers that are not a legal guardian or someone with written authorization at the clinic to make decisions for the child. Clinic staff being a new hire and/or not having

participated directly or indirectly in the implementation of the ACEs Aware screening at their clinic.

b. Rationale for excluding children: We are not recruiting children for data collection during screenings at the clinic visit because their caregiver will report on their behalf based on two screenings (PEARLS and PSC). Child data on referrals to mental health services and socio-demographic characteristics will be obtained directly from the child's clinical chart (EMR system) and after obtaining signed consent and HIPAA authorization forms from each caregiver. *The ACEs screenings are happening at the clinics regardless of this study.*

c. Participants are part of two groups of special populations:

- 1) Clinic Employees: For Aim 2, we will invite clinic personnel to be part of interviews to evaluate the success of our implementation strategies based on their experiences. That means, we will survey them and ask follow-up interview questions assessing their acceptability, feasibility and lessons learned from their experience with the screening process at the clinic.
- 2) Non-English-Speaking Caregivers: For Aim 2, we will randomly select caregivers at each clinic whose children were screened for ACEs to participate in phone interviews about their perceptions of the screening process. We will also gather basic caregiver sociodemographic information (age, gender, education). Spanish-speaking caregivers will be interviewed by a fluent Spanish speaker (e.g., The PI is Latinx scholar and Spanish is her first language). For the child screenings (Aim 1), we will follow the clinics' procedure. That is, when the caregiver makes an appointment for their child, they are asked if they would like a translator. Every clinic has someone who speaks Spanish and two have someone who speaks Arabic. In the event that there would not be a Spanish-speaking staff member available, translation services are available.

IV. Recruitment/Screening Process (sampling strategy)

- a. Recruitment will take place at five Federally Qualified Health Center (FQHC) clinics located in under-resourced communities in California. We do not have exact locations yet because these five clinics will be randomly selected from a total of 28 clinics located in multiple counties (e.g., Riverside, San Bernardino, San Diego).
- b. Recruitment of caregivers for participation in the ACEs screenings and to allow access to their child's EMR data: Once the caregiver checks-in at the front desk, the medical assistant (MA) individual will meet the family and will walk them to the examination room for their wellness visit (part of routine care procedure). As part of this event, the MA will introduce the study and obtain consent from the caregiver for participation. Here, caregivers can decline, in which case the MA will continue with the wellness visit procedure that includes screening for ACEs using the PEARLS tool (this screening is happening at the clinics and regardless of this study). The FQHC's data analyst will receive the list of children who had been screened and consented to be in the study and will provide EMR data to the PI based on the study design schedule. Note: If the caregiver declines to participate in this study, the screener will not use the REDCap programmed tablets as we will not have that caregiver's screening data at all.

Recruitment of caregivers at each clinic for interviews (Aim 2): The caregivers would be informed during initial consent that someone may contact them for a follow up interviews (consent form includes a space to add their phone number for this follow-up contact). A member of our research team will contact selected caregivers to invite them to participate in the follow-up phone interview. Caregivers can decline this follow-up interview at any point. We know caregivers move often or change their phone numbers. We will ask help from the clinic manager in identifying a

current phone number for a caregiver if the one provided in the consent is no longer working. Three attempts will be made to schedule the phone interview with caregivers.

The caregiver consent form will also state that for a group of caregivers selected at random (n=100) they will be contacted 10-weeks after their participation in the study to be asked to follow up questions from the Pediatric Symptoms Checklist (PSC), and about their opinions and experiences with the study, ACEs screening process and suggestions for improvement. Each caregiver will receive a \$50 incentive for participating in the interview. The caregiver consent form also includes language stating that there is a data sharing requirement using a National Data Archive or NDA and per requirement from the federal funding agency.

We will offer the consent form electronically as an option using REDCap to reduce the clinical burden.

From the group of caregivers who are consented at the clinic and who agree to participate in the follow-up interview, the additional recruitment strategies, informed by our clinical partners, are as follows:

- Call caretakers from a local number by obtaining a Google number with each of the clinic's location area code
- The study team members will text caregivers in advance of our interview call so they expect the call. They can reply at that time with "yes" or "no" to confirm. We will add a picture of the flyer.
- Script for the text
 - "Phone call for ACEs interview soon from this number. Text back 'Yes', 'No', or a date to schedule. Flyer attached".

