 - 4.6 Month 4: The PI and consultant ([name]) will pre-record 3 video-training sessions on study procedures and protocols, caregiver consent process and administration of the PSC survey (in 2020, all clinic personnel at the FQHC partner have already completed a 2-hour online training on how to administer the PEARLS screener)

- 4.7 Month 5: Screeners at each selected clinic will go over the videos for training. The PI and [name] will schedule a follow up 45-min call with each screener to discuss videos and learning/questions.
- 4.8 Months 6 – 7.5: Baseline starts in all five selected clinics. Pre-intervention data will be collected from the clinics over a 10-week period. Clinic staff will be told to follow the ACEs state requirements, which include the PEARLS screenings, ACEs-related health conditions checklist, wellness exam, follow-up education, and mental-health referrals if deemed appropriate. Mediators data will be collected at the end of this period.
- 4.9 Months 7.5 to 30 / Trial starts:
 - 4.9.1 During a 10-week trial period for each clinic (data collection will continue until the end of the trial), each clinic switching from control to intervention status will start using the implementation strategies (i.e., support from the trained implementation coach, TIC workgroup guidance/advise, use of electronic tablets for screenings and service referrals).
 - 4.9.2 Due to the human and financial impact of COVID-19 epidemic, the randomized control clinics had not implemented ACEs screening at the time of the pilot starting. We have identified two clinics within the healthcare system, not part of the trial, that have started implementing ACEs screening. These two clinics will serve as non-randomized comparison groups for this study. We will compare our study clinics and these comparison clinics on ACEs screenings and on referrals to mental health services.
 - 4.9.3 Steps for ACEs screenings with caregivers:
 - 4.9.3.a. When a child and their caregiver come to the clinic for the wellness visit, screening staff will conduct the study screenings using a tablet device that has the REDCap database on it. This should take 10 minutes.

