- a. Clinics using implementation strategies will have higher rates of mental health referrals compared to their referral rates before implementing the strategies.
- b. Clinics using implementation strategies will have higher rates of mental health referrals than clinics screening for ACEs and as part of the state funded CALQIC project, without the implementation strategies.
- c. Among children screened, ACEs screenings indicating medium and high risk will lead to mental health referrals at higher rates than screenings indicating low risk.
- d. Exploratory: Are there any differences between in the effect of the implementation strategies on referrals in different sub-groups (such as race, ethnicity, age and gender)?

[figure not shown]
3. Implementation outcomes

- a. Perceive feasibility, acceptability, and usefulness of the intervention will be sufficiently high (see Table 1).

Study design:

Changes to the original study design were needed to accommodate the negative impact that the COVID-19 pandemic had in the partner FQHC system. We conducted a stepped-wedge design (SWD) trial with three sites, with data collection divided into 7 10-week intervals. Study sites remained in the intervention phase for multiple intervals to allow additional data to be collected. In addition to the 3 study sites, 2 additional sites from the same health system served as comparison sites, implementing ACEs screenings without the support of the implementation strategies. See Figure 1 for the SWD schedule.

Figure 1. Stepped-wedge schedule for the ACEs pilot study.

Study sites and patient eligibility:

The study statistician originally selected five clinics from a pool of 16 clinics providing family medicine, pediatric, or primary care for children ages 0 to 5 years old and across five regions to maximize variation (e.g., clinic characteristics such as resources and size). Clinics were located in urban, suburban, rural, and frontier communities. The study PI and FQHC champions invited the identified clinics via email to an informational video session to introduce the study and provided study informational materials to the clinic manager.

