Clinical screening tools	BPSC : 12-item screening measuring children's psychosocial functioning validated for children 0-18 months. Assesses irritability, inflexibility and difficulty with routines. ³ Designed for children 0-18 months; three subscales of four items each. Parents answer questions by selecting one of three responses: "not at all" = 0, "somewhat" = 1, "very much" = 2. Any summed score of 3+ on any of the three subscales indicates that a child is "at risk and needs further evaluation." Scores 0-2 indicates child "appears to meet expectations." Cronbach's alpha adequate for subscales (α =0.75 to 0.83). PPSC : 18-item screening for measurement of children's psychosocial functioning; validated for children ages 18-60 months. Assesses externalizing, internalizing, attention problems, and parenting challenges. ³ Parents select responses as: "not at all"=0; "somewhat"=1; "very much"=2. A score of 9+ indicates children is "at risk and needs further evaluation." α =0.92.	Caregiver
FIM⁴	Self-reported 4-item instrument to evaluate feasibility of implementation efforts. 4-pt Likert scale; average score of	Staff, manager

	4+ shows ACEs policy and implementation strategy perceived as feasible. Good internal consistency ($\alpha=0.89$). Test-retest reliability $r=0.88$.	provider
AIM⁴	Self-reported 4-item instrument to evaluate acceptability of ACEs policy and implementation efforts. 4-pt Likert scale; average score of 4+ shows acceptability. Good internal consistency ($\alpha=0.83$). Test-retest reliability $r=0.83$.	Staff manager provider
Fidelity	The implementation coach will use a checklist to observe the screening staff/providers at each clinic (once in week 5 of each 10-week trial period) to assess adherence to screening protocols and competence of performance. She will identify deviations/concerns and provide immediate feedback. We expect at least 67% fidelity (number of endorsed deviations / all items in the checklist) based on a previous study ⁵ The coach will also document adaptations and emerging challenges and report back to the PI and TIC workgroup. Form will be developed by PI & [name]. Observation checklists/ audits are effective strategies to improve fidelity of performance. ⁶	Implem coach

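### The protocol promises an impact on fidelity, but the coach's score is the only measure and has no comparator, so only a level can be reported

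*Protocol*

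**What the plan says.** Protocol section II (Purpose/Objectives/Aims/Research Questions) states that the study will "examine its impact on the fidelity and reach of ACEs screenings (implementation outcomes". A later objective in the same section is to pilot test fidelity alongside feasibility, acceptability and reach.

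SAP Table 1 gives the only fidelity measure: "The implementation coach will use a checklist to observe the screening staff/providers at each clinic (once in week 5 of each 10-week trial period". The row continues: "She will identify deviations/concerns and provide immediate feedback". It adds that "Observation checklists/ audits are effective strategies to improve fidelity of performance", and sets an expected level of at least 67%.

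The coach belongs to the strategy under test. Activity 2 in Protocol section II reads "Each clinic will receive intense implementation support from the FQHC implementation coach". Protocol V.1, step 4.9.1, ties the start of that support to the crossover: "each clinic switching from control to intervention status will start using the implementation strategies (i.e., support from the trained implementation coach". The two comparison sites are described in the SAP, Study design, as "implementing ACEs screenings without the support of the implementation strategies".

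The SAP hypotheses on reach and referrals are comparative (1a, 1b, 2a, 2b). Hypothesis 3 covers feasibility, acceptability and usefulness and does not name fidelity. The SAP's Statistical analysis section models reach and referrals only. The protocol's comparison with the non-randomized clinics is limited to screenings and referrals.

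**The concern.** An impact is a difference between a state with the strategy and a state without it. Here the person who measures fidelity arrives with the strategy, so on the most natural reading no score exists for the state without it. A percentage observed during intervention intervals could then be reported as meeting an objective about impact, although nothing in the trial shows what fidelity would have been otherwise.

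A second question follows from the timing, "once in week 5 of each 10-week trial period". If that includes intervals before a clinic's switch, the coach would have observed control clinics and given feedback on the spot. By the SAP's own account such observation improves performance, so a piece of Activity 2 would have reached the control intervals used for hypotheses 1a and 2a, which concern the primary outcomes.

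**Working it through.** The documents give no sample size, expected difference or test for fidelity, so there is no planned figure to reproduce. The check is a search for a comparator, then a count.

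**Step 1. Where a comparator could come from**

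| Possible source | What the documents provide |
|---|---|
| Control intervals at study sites | Protocol V.1, step 4.8, describes baseline under state requirements; no coach and no fidelity observation is mentioned |
| Comparison clinics | No strategy, hence no coach; comparisons cover screenings and referrals |
| Another assessor | None described |
| Planned contrast | None in the SAP hypotheses or Statistical analysis |
| Fixed benchmark | 67%, from a cited study: a level, not a difference |

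**Step 2. Counting observations**

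Inputs: 3 study sites and 7 ten-week intervals (SAP, Study design); 1 observation per period, in week 5 (SAP Table 1). The schedule figure is not in the text available, so let K be the total number of control clinic-intervals. The ceiling is 3 × 7 × 1 = 21 observations.

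- *Observation in intervention intervals only.* Intervention scores: 21 − K. Control scores: 0. Comparison-clinic scores: 0. This holds for every K.
- *Observation in all intervals.* Control scores: K. Only the first at each clinic precedes any feedback, so at most 3 × 1 = 3 control scores are free of earlier feedback, whatever the schedule. An unblinded person who also delivers the strategy would have scored them.

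On the second reading, the share of control clinic-weeks that fall after feedback is (10K − 3 × 5) / 10K. The outer limits assume that every site has at least one control and one intervention interval and that feedback comes at the end of week 5:

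- K = 3: (30 − 15) / 30 = 50%
- K = 18: (180 − 15) / 180 = 92%

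This is the share of control time that would be exposed. It is not an estimate of bias in reach or referrals, for which the documents give no basis.

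**Step 3. Which reading the text favours**

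- For intervention intervals only: Protocol section II places the coach's intense support in the first crossover period and lighter support in the periods after it. Steps 4.8 and 4.9 separate baseline from the trial, and step 4.9.1 links a clinic's trial period to its switch.
- For all intervals: the Mental health referrals row of SAP Table 1 uses the same term for the window over which referrals are counted. Hypothesis 2a needs that window before the strategies as well as after.

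The first reading is more likely, but the same term carries both meanings within one table.

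**Step 4. The benchmark**

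Table 1 writes the fidelity ratio with endorsed deviations in the numerator and all checklist items in the denominator. Taken literally, at least 67% means that at least 67% of items were deviations and at most 100% − 67% = 33% were followed. The intended ratio is presumably the reverse.

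**The case against.** The strongest reply is that this is one loose word in a purpose statement. The pilot objective and the 67% level treat fidelity descriptively, the SAP claims no fidelity effect, and its primary outcomes are reach and referrals. That stands as far as the SAP is concerned, and it limits the seriousness of the point. It does not remove the mismatch, because the protocol names fidelity beside reach as an outcome on which an impact will be examined.

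A reader might infer that coaching did leak into control intervals and shrank the contrasts in hypotheses 1a and 2a. The documents do not support that. No text places the coach in a control clinic, and the favoured reading keeps the coach out.

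A reader might also infer that no screening was under way in control intervals, so fidelity could not have been observed there. That too goes further than the text. The protocol says screening had not been implemented when the pilot started, not throughout the control periods, and its rationale for excluding children says screening takes place regardless of the study. If there was nothing to observe, there was also little for the coach to give feedback on, so this inference weakens the leakage argument.

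Finally, one might try to rescue an impact by comparing how often the state conditions checklist is recorded in the medical record. That would not be like for like: Table 1 names the medical record as its source, but providers at intervention clinics complete the checklist on the REDCap tablet. Comparison-clinic data arrive as aggregated numbers.

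**Conclusion.** The point holds as a mismatch between a stated objective and what the design can deliver. With the coach as sole assessor and no fidelity contrast planned, the study can report a fidelity level in intervention intervals against a benchmark. It cannot report an impact. This conclusion needs no assumption about the crossover schedule: comparator scores number 0 on the likely reading and, even on the other, at most 3 are free of earlier feedback.

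The effect on hypotheses 1a and 2a is conditional. It arises only if observation with feedback took place before a switch, which the documents leave open but do not suggest. Its size is unknown; the 50% to 92% range describes exposed control time under assumed schedules and nothing more. No fixed split of control and intervention observations should be quoted, because the schedule is not available.

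**What to change.** - **Protocol section II.** Limit the word impact to reach and the other outcomes that are contrasted, and state that fidelity is described in intervention intervals only.
- **SAP Table 1, Fidelity row.** State that the observation belongs to intervention intervals. The SAP describes the trial as already conducted, so rewording cannot change what was done: also report the dates of the observations by clinic and interval.
- **If any observation preceded a switch.** Report it as a limitation of hypotheses 1a and 2a, and add a sensitivity analysis that excludes a clinic's control data collected after that feedback.
- **The 67% target.** Express it as checklist items adhered to over all items.

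The cost is wording in two documents and a short table of observation dates. The sensitivity analysis, if needed, would rest on fewer and earlier control data and would be less precise. The downside is that the protocol gives up an impact claim on fidelity that it cannot support.
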